	
21. Subject is known to be noncompliant or is unlikely to comply with the requirements of the trial protocol (e.g., due to alcoholism, drug dependency, mental incapacity) in the opinion of the investigator.

Trial Procedures	
ADX-629-PS-001 will consist of 7 visits: 5 in-person visits and 2 phone calls. At every in-person visit, assessments should be completed in the following order: vital signs, subject self-evaluation (Patient Global Impression of Change [PGIC]), clinical evaluations (IGA first, then BSA and PASI), and then remaining assessments.
 
Visit 1 (Day -21 to -3): Screening. Subjects can be screened up to 21 days prior to Baseline. If applicable, qualified subjects can washout from prohibited medications and/or therapies prior to Baseline (after obtaining informed consent). Subjects who require washout for longer than 30 days will be reconsented.
 
The trial requirements and procedures will be reviewed and written informed consent must be obtained prior to the initiation of any trial-related procedures. Demographics, inclusion/exclusion criteria, medical history, and concomitant medications and concurrent procedures/therapies will be reviewed to determine eligibility. Vital signs will be measured. Clinical evaluations (IGA first, then BSA and PASI) will be performed by the investigator. A physical examination and electrocardiogram (ECG) will be performed. Blood and urine samples will be taken for serology, clinical laboratory tests (chemistry, hematology, and urinalysis), and a UPT for all females (test results must be negative for the subject to be eligible for the trial). If fasting samples cannot be collected at this time, the subject may return to the clinic for sample collection such that the results of the clinical laboratory tests are available for review prior to Visit 2/Baseline. The subject will be scheduled for Visit 2.
 
Visit 2 (Day 1): Baseline. The subject will return to the clinic and be queried for any changes in health status since the previous visit, including concomitant medications and concurrent procedures/therapies. Eligibility will be confirmed. Vital signs will be measured. Clinical evaluations (IGA first, then BSA and PASI) will be performed by the investigator. Physical examination and an ECG will be performed. Blood samples will be taken for baseline blood biomarker analysis (prior to first test article administration) and clinical laboratory tests (chemistry, hematology), and urine samples will be taken for urinalysis and UPT for WOCBP (post-menopausal status must also be confirmed with FSH test results from Visit 1/Screening; UPT results must be negative for the subject to be eligible for the trial). Non-invasive skin samples will be collected from non-lesional (perilesional) and lesional skin.
 
Subject Instruction Sheet will be dispensed. Test article accountability will be documented. The first dose will be administered at the site under supervision of trial staff. Adverse events (AEs) will be recorded. The subject will be scheduled for the next visit.
 
Visit 3 (Day 15 ± 2): Phone Call. The site staff will contact the subject by telephone and query the subject for any changes in health status, including

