
	
concomitant medications and concurrent procedures/therapies. The site staff will remind the subject to continue to take 1 tablet twice daily until the next clinic visit. Any AEs will be discussed with the investigator to determine if the subject should return to the study site for an unscheduled visit. The next visit will be confirmed.
 
Visit 4 (Day 29 ± 3): Week 4. One day prior to the visit, the site staff will contact the subject to remind them that if the subject chooses to take the morning dose of test article at home on the day of their clinic visit, the subject should: 1) take the morning dose of test article approximately 2 hours prior to the study visit AND 2) note the time of dosing on the Subject Instruction Sheet. Subject will also be informed that if the subject chooses to take the morning dose of test article in the clinic, the subject will need to remain in the clinic for 2 hours after dosing.
 
On the day of the visit, the subject will return to the clinic and be queried for any changes in health status since the previous visit, including concomitant medications and concurrent procedures/therapies. Vital signs will be measured. Subject evaluation (PGIC) will be performed by the subject and clinical evaluations (IGA first, then BSA and PASI) will be performed by the investigator. A targeted physical examination based on subject symptoms and an ECG will be performed. A non-invasive skin sample will be collected from lesional skin (same area collected at baseline). Test article accountability will be documented. Subjects who did not take their morning dose at home will take the morning dose of test article under supervision of study staff and will wait 2 hours before blood and urine sample collection. Time of dosing will be recorded. Blood samples will be taken for biomarker analysis (including drug metabolism) and clinical laboratory tests (chemistry, hematology) and urine samples will be taken for urinalysis, a UPT (for WOCBP), and urine drug metabolite analysis between 2 and 4 hours after test article dosing. Subject will be reminded to continue to take 1 tablet twice daily until the next clinic visit. AEs will be recorded. The subject will be scheduled for the next visit, as appropriate.
 
Visit 5 (Day 57 ± 3): Week 8. One day prior to the visit, the site staff will contact the subject to remind them to note the time of dosing on the Subject Instruction Sheet if the subject chooses to take the morning dose of test article on the day of their clinic visit at home and to inform them that if the subject chooses to take the morning dose of test article in the clinic, the subject will need to remain in the clinic for 1 hour after dosing.
 
On the day of the visit, the subject will return to the clinic and be queried for any changes in health status since the previous visit, including concomitant medications and concurrent procedures/therapies. Vital signs will be measured. Subject evaluation (PGIC) will be performed by the subject and clinical evaluations (IGA first, then BSA and PASI) will be performed by the investigator. A targeted physical examination based on subject symptoms and an ECG will be performed. Test article accountability will be documented. Subjects who did not take their morning dose at home will take the morning dose of test article under supervision of study staff and will wait 1 hour before blood sample collection. Time of dosing will be recorded. Blood samples will be taken for biomarker analysis and clinical laboratory

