### **6.2 Instructions for Use and Administration**

Subject kits will contain bottles containing tablets of test article. The first dose will be taken at the clinic on Day 1. Note: If subject's Day 1 visit is in the evening (i.e., later in the day), and the subject is unlikely to have at least an 8-hour separation between the dose taken at the clinic and the second Day 1 dose, then the dose taken at the clinic will be considered their evening dose and the subject will not dose again until the following morning. Subjects will be instructed to take 1 tablet by mouth twice daily for 12 weeks, once in the morning and once in the evening, with at least 8 hours and preferably 12 hours between doses. Each subject will be provided with a Subject Instruction Sheet providing further dosing details (see Appendix 2).

**For Visit 4**, the morning dose of test article may be taken by the subject at home or may be taken at the site under supervision of the site staff. One day prior to the visit, the site staff will contact the subject to remind them that if the subject chooses to take the morning dose of test article at home on the day of their clinic visit, the subject should: 1) take the morning dose of test article approximately 2 hours prior to the study visit AND 2) note the time of dosing on the Subject Instruction Sheet. Subject will also be informed that if the subject chooses to take the morning dose of test article in the clinic, the subject will need to remain in the clinic for 2 hours after dosing. Time of dosing will be recorded, such that time (in minutes) from test article dosing to blood draw for blood biomarker analysis and urine draw for drug metabolism analysis can be calculated.

**For Visit 5 and Visit 6**, the morning dose of test article may be taken by the subject at home or may be taken at the site under supervision of the site staff. One day prior to the visit, the site staff will contact the subject to remind them to note the time of dosing in the Subject Instruction Sheet if the subject chooses to take the morning dose of test article on the day of their clinic visit at home and to inform them that if the subject chooses to take the morning dose of test article in the clinic, the subject will need to remain in the clinic for 1 hour after dosing. Time of dosing will be recorded, such that time (in minutes) from test article dosing to blood draw for blood biomarker analysis can be calculated.

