### 9.2 Visit 2 (Day 1): Baseline

*Prior to this visit, the investigator or designee will:*

- Review laboratory results to determine if subject is eligible to enroll in the trial.

*At this visit, the investigator or designee will:*

- Query the subject for any changes in health status since the previous visit, including concomitant medications and concurrent procedures/therapies, and document the findings.
- Confirm I/E criteria.
- Review and update medical history, if needed.
- Measure vital signs (see Section 10.7.1).
- Perform clinical evaluations (IGA first, then BSA and PASI). See Section 10.3, Section 10.5, and Section 10.4, respectively.
- Perform a brief physical exam (see Section 10.7.2). Record any findings in medical history.
- Perform ECG (see Section 10.7.3).
- Collect blood for baseline blood biomarker analysis (RASP ELISAs and cytokines) prior to first test article administration (see Section 12.3).
- Collect blood and urine samples for clinical laboratory tests (chemistry, hematology, and urinalysis). If possible, subjects should be fasting for approximately 8 hours.
- Perform a UPT for all WOCBP. The result must be negative for the subject to be enrolled in the trial.
- Identify a lesion area for skin sampling (this location will be used for all subsequent assessments during the study). Collect non-invasive skin samples from lesional and non-lesional (perilesional to the lesional sample) skin (see Section 12.2).  
**Note:** Be sure to capture and document location of collection for future collections.
- Dispense Subject Instruction Sheet.
- Document Test Article Accountability and dispense the test article.
- Supervise the first dose of test article in the clinic.
- Document any AEs.
- Schedule the next visit.

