### 9.3 Visit 3 (Day 15 ± 2): Phone Call

*During this phone call, the investigator or designee will:*

- Query the subject for any changes in health status since the previous visit, including concomitant medications and concurrent procedures/therapies, and document the findings.
- Remind the subject to continue to take 1 tablet twice daily until the next clinic visit.
- Discuss any AEs to determine if the subject should return to the study site for an unscheduled visit.

 WOCBP include any female who has experienced menarche or is 10 years of age or older and who has not undergone successful surgical sterilization (hysterectomy, bilateral tubal ligation, salpingectomy, or bilateral oophorectomy at least 26 weeks prior to Visit 2/Baseline) or is not postmenopausal (defined as amenorrhea for at least 1 year in women 50 years of age and older). Post-menopausal status must also be confirmed with FSH test results from Visit 1/Screening.

- Confirm the next visit.

#### 9.4 Visit 4 (Day 29 ± 3): Week 4

**One day prior to the visit, the site staff will contact the subject to remind them that if the subject chooses to take the morning dose of test article at home on the day of their clinic visit, the subject should: 1) take the morning dose of test article approximately 2 hours prior to the study visit AND 2) note the time of dosing on the Subject Instruction Sheet. Subject will also be informed that if the subject chooses to take the morning dose of test article in the clinic, the subject will need to remain in the clinic for 2 hours after dosing.**

*At this visit, the investigator or designee will:*

- Query the subject for any changes in health status since the previous visit, including concomitant medications and concurrent procedures/therapies, and document the findings.
- Measure vital signs (see Section 10.7.1).
- Have the subject perform the subject evaluation (PGIC). See Section 10.6.
- Perform clinical evaluations (IGA first, then BSA and PASI). See Section 10.3, Section 10.5, and Section 10.4, respectively.
- Perform a targeted physical exam (see Section 10.7.2). Record any new or worsening clinically significant abnormalities as AEs.
- Perform ECG (see Section 10.7.3).
- From the same area collected at baseline, collect non-invasive skin sample from lesional skin for subjects (see Section 12.2).
- Review compliance.
- Document Test Article Accountability; all test articles will be collected and tablets will be counted.

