- If the subject chose to take the test article in the clinic, administer the morning dose of test article to the subject.
- Record dosing time. Note: dosing time can be obtained verbally from the subject, from the Subject Instruction Sheet, or from administration in the clinic.
- Collect blood for blood biomarker analysis (metabolite analysis, RASP ELISAs, and cytokines) **between 2 and 4 hours after** test article administration (see Section 12.3).
- Collect blood and urine samples for clinical laboratory tests (chemistry, hematology, and urinalysis). If possible, subjects should be fasting for approximately 8 hours.
- Collect urine sample for urine drug metabolism analysis **between 2 and 4 hours after** test article administration (see Section 12.4).
- Perform a UPT for all WOCBP. The result must be negative for the subject to continue dosing with test article.
- Document any AEs.

- Schedule the next visit.

### 9.5 Visit 5 (Day 57 ± 3): Week 8

**One day prior to the visit, the site staff will contact the subject to remind them to note the time of dosing in the Subject Instruction Sheet if the subject chooses to take the morning dose of test article on the day of their clinic visit at home and to inform them that if the subject chooses to take the morning dose of test article in the clinic, the subject will need to remain in the clinic for 1 hour after dosing.**

*At this visit, the investigator or designee will:*

- Query the subject for any changes in health status since the previous visit, including concomitant medications and concurrent procedures/therapies, and document the findings.
- Measure vital signs (see Section 10.7.1).
- Have the subject perform the subject evaluation (PGIC). See Section 10.6.
- Perform clinical evaluations (IGA first, then BSA and PASI). See Section 10.3, Section 10.5, and Section 10.4, respectively.
- Perform a targeted physical exam (see Section 10.7.2). Record any new or worsening clinically significant abnormalities as AEs.
- Perform ECG (see Section 10.7.3).
- Review compliance.
- Document Test Article Accountability; all test articles will be collected and tablets will be counted.
- If the subject chose to take the test article in the clinic, administer the morning dose of test article to the subject.
- Record dosing time. Note: dosing time can be obtained verbally from the subject, from the Subject Instruction Sheet, or from administration in the clinic.

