#### **14.2 Adverse Event Details**

[figure not shown]
AEs may be either spontaneously reported or elicited during questioning and examination of a subject. All AEs must be recorded on the AE eCRF. If known, the investigator should report the diagnosis of the underlying illness or disorder, rather than its individual symptoms. Subjects experiencing AEs that cause interruption or discontinuation of test article or those experiencing AEs that are present at the end of their participation in the trial should receive follow-up as appropriate. AEs should be followed to resolution or stabilization (if possible) and, if they become serious, reported as serious adverse events (SAEs, see Section 14.4). If possible, the outcome of any AEs that caused permanent discontinuation or that were present at the end of the trial, especially those considered by the investigator to be related to the test article, should be reported.

Information on the medical condition of subjects should begin following the subject’s written informed consent to participate in the trial and a medical history should be taken at screening. During any wash out and screening periods, any changes in the health of subjects should be recorded as changes in medical history unless an event occurred as a result of a trial-related procedure and is unanticipated; in such cases, the event should be recorded as an AE and reported to the Institutional Review Board (IRB) as an “unanticipated problem” in accordance with local procedures. Other changes in subject health information becomes AE data when the subject begins dosing with the test article; therefore AE data should be

collected from the date of the first dose of test article until the date of the final trial visit. These data are considered treatment-emergent AEs.

In clinical trials in healthy humans exposed to ADX-629, AEs deemed unrelated to test article included sinus congestion, headache, nasal congestion, upper respiratory tract infection, and rhinitis. One AE deemed possibly related to test article included syncope of moderate intensity.

The investigator will instruct the subject to report any AEs that may occur during the trial. At each visit, the investigator should ask the subject, in non-directive fashion, about any change in the subject's overall health status since the previous visit.

The investigator must determine the relationship of the AE to the test article according to the following categories:

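### Vital signs and ECGs at Visits 4–6 are read before the dose in subjects who dose in clinic and after it in those who dose at home, and the SAP pools both.

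*Protocol*

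**What the plan says.** **Order of assessments.** The Protocol Synopsis (Trial Procedures) sets a sequence for clinic visits: "At every in-person visit, assessments should be completed in the following order: vital signs, subject self-evaluation", followed by the investigator's gradings and then everything else. The ECG is not named in that rule and falls in the last group.

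**Place of the dose.** Section 6.2 leaves the place to the subject on the days of Visits 4, 5 and 6: "the morning dose of test article may be taken by the subject at home or may be taken at the site". For Visit 4, a subject dosing at home is told to "take the morning dose of test article approximately 2 hours prior to the study visit". For Visits 5 and 6 the visible text asks only that the time of a home dose be noted.

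**Sequence within the visit.** In Sections 9.4, 9.5 and 9.6 vital signs come near the top of the list, the ECG follows the gradings and physical examination, and only later comes the instruction "If the subject chose to take the test article in the clinic, administer the morning dose of test article to the subject". The synopsis has the same sequence: "Subjects who did not take their morning dose at home will take the morning dose of test article under supervision of study staff" stands after the ECG and before blood sampling. At Visit 2 (Section 9.2) vital signs and ECG precede "Supervise the first dose of test article in the clinic", and no later reading that day is listed.

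**Timing rules.** Sections 10.7.1 and 10.7.3 set rest conditions only. Section 6.2 has dose time recorded so that the interval to the blood draw (and at Visit 4 the urine sample) can be calculated. It does not mention vital signs or ECG.

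**Analysis.** SAP 8.8.5 and 8.8.6 summarise vital signs and ECG parameters as observed values and changes from Baseline, plus a shift table for ECG interpretation. Neither uses place of dosing or time since dose.

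**The concern.** Changes from Baseline in vital signs and in ECG interpretation are two of the four safety endpoints (Protocol 17.2.1), in a trial that Section 17.1 describes as mainly about safety and tolerability. At the same nominal visit, one subject may be read at the end of a dosing interval and another about 2 h into one. The choice may change from visit to visit, so a single subject's course can mix the two states as well.

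An effect on blood pressure, heart rate or an ECG interval that follows drug level would be largely unseen in clinic dosers and diluted in the pooled mean by an unknown amount. With about 10 subjects and no control arm, nothing offsets this. A reassuring mean change could reflect a lack of effect or simply pre-dose readings, and the planned tables could not tell these apart.

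**Working it through.** The plan gives no figure for the time from dose to vital signs or ECG, so there is none to reproduce. The check has two parts.

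**1. Time since last dose when vital signs and ECG are read, following the listed sequence**

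| Visit | Dose in clinic | Dose at home |
|---|---|---|
| 2 (Day 1) | before any dose | not applicable |
| 4 | about 8–12 h after the evening dose | about 2 h after the morning dose |
| 5, 6 | about 8–12 h after the evening dose | not set in the visible text |

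The 8–12 h range is the minimum and preferred dosing interval in Section 6.2. The Day 1 readings give a drug-free Baseline, as intended (SAP Section 5), but no post-dose reading.

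**2. Size**

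Inputs: mean half-life of 3.49 to 6.83 h in multiple-day exposure (Protocol Section 1); 12 h or 8 h since dose for clinic dosers; 2 h for home dosers at Visit 4; N = 10.

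With first-order decline, the level at *t* hours relative to the level at 2 h is 2^(−(*t* − 2)/half-life).

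- 12 h, half-life 3.49 h: 2^(−10/3.49) = 0.137
- 12 h, half-life 6.83 h: 2^(−10/6.83) = 0.362
- 8 h, half-life 3.49 h: 2^(−6/3.49) = 0.304
- 8 h, half-life 6.83 h: 2^(−6/6.83) = 0.544

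So a clinic doser is read at 14–36% of the 2 h level with a 12 h interval, or 30–54% with an 8 h interval.

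Now assume, for illustration, that effect is proportional to level, that clinic dosers are at 12 h and that home dosers are at 2 h. With *k* of 10 subjects dosing at home, the pooled mean as a share of the 2 h effect is [*k* + (10 − *k*) × ratio]/10.

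| Home dosers | Half-life 3.49 h | Half-life 6.83 h |
|---|---|---|
| 0 of 10 | 0.137 | 0.362 |
| 5 of 10 | (5 + 5 × 0.137)/10 = 0.569 | (5 + 5 × 0.362)/10 = 0.681 |
| 10 of 10 | 1.000 | 1.000 |

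The documents do not say how many subjects will dose at home, so the whole range applies.

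**The case against.** **The order rule does not mention dosing.** This stands in part. The synopsis rule ranks assessments against each other and does not name the dose or the ECG. A reader might infer that a pre-dose ECG is mandated. It is not: the ECG's place comes only from the listed order, and a site could record it during the 1–2 h wait after an in-clinic dose without breaking the rule. For vital signs the case is firmer. They must precede every other assessment, and both visit descriptions put the dose after several of these. The freedom over the ECG adds variation between sites and does not remove the mixing.

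**The timing may be set elsewhere.** The Schedule of Events and the Subject Instruction Sheet (Appendix 2) could not be read in the copy used, and the eCRF is not included. A timing note, a set home-dose time for Visits 5–6 or a field for clock times cannot be excluded. This stands as a caveat.

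**Clinic dosers are not unobserved after dosing.** Correct. Blood and urine samples are listed after the dose, subjects stay on site for 1–2 h, and adverse events are documented late in each visit, including Day 1. The gap concerns scheduled vital signs and ECGs only.

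**The link to syncope is an inference.** Section 14.2 reports that "One AE deemed possibly related to test article included syncope of moderate intensity". A reader might conclude that this was a near-peak haemodynamic effect that the schedule would miss. The text gives no dose, time since dose or blood pressure for that event, and vital signs here are taken seated after rest. The event is a reason for interest in post-dose readings, not evidence that re-timing would detect the risk.

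**The analysis is descriptive and Phase 1 tested higher doses.** True: no test depends on these readings. But the descriptive tables are the safety result of this trial, and the highest multiple dose in Phase 1 was given for 10 days, against 12 weeks here.

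**Conclusion.** The point holds, as a moderate weakness that is cheap to repair. As written, vital signs and ECG changes at Visits 4–6 combine readings 8–12 h after a dose with readings about 2 h after one (Visit 4) or at an unset time (Visits 5–6). The SAP does not separate them.

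The difference in drug level is large: 14–36% of the 2 h level at 12 h, or 30–54% at 8 h. The resulting dilution of the pooled mean ranges from severe (14–36% of the 2 h effect shown) to none (100%), depending on how many subjects dose at home; at an even split it is 57–68%. These shares rest on first-order decline and on effect proportional to level, which the documents do not establish. They apply to Visit 4, because home-dose timing at Visits 5–6 is not set. They are also relative to the 2 h level. A reader might want them as shares of the peak effect, but the visible text gives no time of peak.

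**What to change.** **Protocol, Visit 4.** Take vital signs and ECG for all subjects in the 2–4 h post-dose window already used for blood and urine. Home dosers arrive at about that point, and clinic dosers already wait 2 h, so this adds no visit, procedure or waiting time and changes no dose. The small downside is that vital signs no longer come first at Visit 4, so the synopsis order needs an exception.

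**Protocol, Visits 5–6.** The 1 h wait binds only subjects who dose in clinic, so moving the readings after it would leave home dosers at unset times. Record clock times for vital signs and ECG, and have the sponsor state one timing relative to dose for all subjects.

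**SAP 8.8.5 and 8.8.6.** List time since last dose beside each reading, and show vital sign and ECG changes by pre-dose or post-dose status. This costs one derived variable and a split of existing tables, provided clock times are captured. Reading times that were not recorded cannot be reliably recovered later.

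**Confirmation.** The sponsor should confirm that the Schedule of Events carries no timing note; if it does, Sections 9.4–9.6 should be aligned with it.

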## **12.4 Urine Drug Metabolite Analysis**

At Visit 4 only, urine samples will be taken from subjects between 2 and 4 hours after test article dosing and sent to Charles River Laboratories (Mattawan, MI) for urine drug metabolite analysis.

Further details will be provided in a laboratory manual.

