#### **14.6 Pregnancy**

WOCBP (see Schedule of Events for definition of WOCBP) must have a UPT prior to trial enrollment. Post-menopausal status must also be confirmed with FSH test results from Visit 1/Screening. Prior to trial enrollment, WOCBP must be advised of the importance of avoiding pregnancy during the trial and the potential risk factors for an unintentional pregnancy. The subject must sign an informed consent form documenting this discussion.

WOCBP should be instructed to contact the investigator immediately if they suspect they might be pregnant (e.g., missed or late menstrual period). If a subject or investigator suspects that a subject may be pregnant at any time during the trial, the test article must be withheld until the results of laboratory pregnancy testing are available. If pregnancy is confirmed, the subject must not receive or administer further test article and must be discontinued from the trial unless the Medical Monitor elects to retain the subject for all or part of the remaining trial period to follow the subject for safety.

If following initiation of trial treatment, it is subsequently discovered that a subject was pregnant or may have been pregnant at the time of test article exposure, the investigator must immediately notify the Medical Monitor and record the pregnancy on the appropriate pregnancy surveillance form. The form will be sent to TI. The investigator will also report

any pregnancy associated with the trial treatment as required by their IRB and keep careful source documentation of the event.

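### The Visit 4 synopsis puts the pregnancy test after the in-clinic dose, so the test cannot stop that dose; Section 9.4 permits testing first but does not require it

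*Protocol*

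**What the plan says.** **Synopsis, Trial Procedures, Visit 4.** A subject who did not take the morning tablet at home takes it under supervision and "will wait 2 hours before blood and urine sample collection". The collection that follows is described in one sentence: "urine samples will be taken for urinalysis, a UPT (for WOCBP), and urine drug metabolite analysis between" 2 and 4 hours after the dose.

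**Section 9.4 (Visit 4).** The list has a separate item, "Collect urine sample for urine drug metabolism analysis", carrying the 2 to 4 hour window, and the biomarker blood carries the same window. The UPT is its own item with no time attached: "Perform a UPT for all WOCBP. The result must be negative for the subject to continue dosing with test article". The in-clinic dose is listed earlier than the UPT, but the list is not stated to be a required order.

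**Section 12.4.** Under the metabolite heading only, "urine samples will be taken from subjects between 2 and 4 hours after test article dosing".

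**Section 9.2 (Visit 2).** For the UPT, "The result must be negative for the subject to be enrolled in the trial"; later in the same list comes "Supervise the first dose of test article in the clinic".

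**Section 14.6.** When pregnancy is suspected, "the test article must be withheld until the results of laboratory pregnancy testing are available".

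**The concern.** A scheduled pregnancy test during treatment is there to find a pregnancy that nobody suspects; Section 14.6 already deals with a suspected one. Section 6.3 states that the effects of the drug in pregnant women and unborn children are not known. Visit 3 is a phone call, so Visit 4 carries the first scheduled UPT since Baseline. At that visit, staff hold the returned tablets and supervise the dose themselves, so it is easy to hold the tablet until the result is read. A site that follows the synopsis gives the tablet at least 2 hours before it collects the urine for the test.

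The stake is a small safety matter: one avoidable dose in a woman with an undetected pregnancy. It does not touch any estimate or analysis.

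**Working it through.** The plan gives no figure for this point, so the check is a comparison of texts followed by a count of doses.

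**1. Does the synopsis force the order at Visit 4?** The sentence listing the urine tests could, on its own, be read as applying the 2 to 4 hour window only to its last item, the metabolite urine. The preceding sentence rules that out: for in-clinic dosers the 2-hour wait covers blood and urine, with no exception for the UPT. As worded, the synopsis puts the test after the dose.

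**2. Does the body of the protocol force it?** No. Sections 9.4 and 12.4 time the metabolite urine, and 9.4 also times the biomarker blood. Neither times the UPT. The general rule in the synopsis fixes the order of assessments only as far as the clinical evaluations and leaves the rest open. A site working from 9.4 may test first.

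**3. Is it the same at Visits 5 and 6?** No. In the synopsis the wait there is 1 hour and covers blood only. The in-clinic dose is listed before the UPT in the synopsis and in Sections 9.5 and 9.6, but nothing ties the urine to the dose. Testing first is allowed and not required, as in 9.4.

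**4. Who is affected?** A woman who doses at home is told to do so about 2 hours before Visit 4, so she too has taken that tablet before the test. Only the in-clinic dose can be held back by a test at the site.

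**5. How much drug is at stake?** Inputs are twice-daily dosing, one 250 mg tablet per dose, and Visit 4 at Day 29 ± 3. Full compliance and two doses on Day 1 are assumed.

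- Doses before the visit-day morning dose = 2 × (day − 1).
- Day 29: 2 × 28 = 56, so the in-clinic tablet is dose 57.
- Day 26: 2 × 25 = 50, so dose 51. Day 32: 2 × 31 = 62, so dose 63.
- If only the evening dose was taken on Day 1, each number falls by one: dose 56 (50 to 62).
- Days since the Baseline UPT: 29 − 1 = 28 (26 − 1 = 25 to 32 − 1 = 31).

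**6. What share of the exposure since conception is that?** The conception date is an assumption. If it is k days before a Day 29 visit, doses since then, including the in-clinic one, number 2k + 1.

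- k = 14: 29 doses, so 1/29 = 3.4%.
- k = 28: 57 doses, so 1/57 = 1.8%.

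**The case against.** The strongest reply is that the detailed procedures already settle this: Section 9.4 leaves the UPT untimed, and the synopsis has merely compressed three urine tests into one sentence. That is right as to the source of the problem. A reader might infer that the protocol as a whole requires dosing before testing, and the documents do not support that. What remains is that the two places can be followed differently on a pregnancy safeguard, and 9.4 does not instruct the site to test first.

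A second reply is that the design openly accepts a visit-day dose before the test, because home dosers take one, and that a negative result to continue dosing can be read as governing later doses only. This also stands. It would go too far to say that the synopsis breaches the 9.4 rule, or that testing first would close the gap for all WOCBP. The dose taken at home is out of reach; the supervised one is not.

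A third reply is that the Visit 2 comparison is loose, since that test decides entry before any exposure, whereas Visit 4 is monitoring after about 56 doses. That is fair, and the point does not depend on the comparison.

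Finally, inclusion criterion 3 requires negative tests at Screening and Baseline and, for WOCBP, highly effective contraception. An unsuspected pregnancy at Visit 4 should be rare. This limits the size of the point without removing it.

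**Conclusion.** The point holds as a minor one. The Visit 4 synopsis orders events so that the scheduled UPT cannot prevent the supervised dose, and nothing in the documents gives a reason to delay that test. The size is one 250 mg tablet, about dose 57 (51 to 63 across the visit window), in a WOCBP who has an unsuspected pregnancy and doses in clinic. Under the assumed conception dates that is 1.8% to 3.4% of her doses since conception. The documents do not state how many of the approximately 10 subjects will be WOCBP, or how many of them will dose in clinic, so the plan does not show that any subject will be affected.

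No endpoint, population or summary changes. The contents of the Schedule of Events and of the Subject Instruction Sheet (Appendix 2) are not reproduced in the text available, so the conclusion covers the written procedures only.

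**What to change.** In the Visit 4 synopsis, remove the UPT from the post-dose urine collection. State that for WOCBP who dose in clinic the on-site UPT is done after the clinical evaluations, which respects the fixed assessment order, and must be negative before the supervised dose. Keep the 2 to 4 hour window for the metabolite urine and for the biomarker and metabolite blood. The window runs from the dose, so testing first does not disturb it.

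For consistency, put the same instruction, a UPT before any in-clinic dose, in Sections 9.4 and 9.5, and in 9.6 if desired. The current text there allows that order without requiring it, and a rule added at Visit 4 alone would be hard to justify.

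**Cost.** One extra urine sample at Visit 4 for WOCBP who dose in clinic, and the time to read the test. These women must be tested on site, so the reference-laboratory option in Section 12.5 is closed to them. UPT kits (Section 16.2) and urine containers (Section 16.3) are already listed as supplies. The wording change is a protocol amendment and needs IRB approval before use (Section 18.4).
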